5.2. Baseline Definitions

For all endpoints (except as noted in baseline definitions) the baseline value will be the latest pre-dose assessment with a non-missing value, including those from unscheduled visits. If time is not collected, Day 1 assessments are assumed to be taken prior to first dose and used as baseline. If no central lab value is available, the latest non-missing pre-dose value from local lab will be used. If there are multiple assessments on the same day, the mean will be used as the baseline value.

Unless otherwise stated, if baseline data is missing no derivation will be performed and baseline will be set to missing.

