11	sCR/CR/VGPR/PR/MR	PD (any reason) OR No subsequent disease assessment: subject died or discontinued study or started new anti-cancer therapy before further adequate disease assessment	SD
12	sCR/CR/VGPR/PR/MR/PD (due to reasons other than imaging, i.e., plasmacytoma or bone lesion)	No subsequent disease assessment: subject has not died, discontinued from study or (except for PD) started new anti-cancer therapy; but as yet has no further adequate disease assessments	Unconfirmed sCR/CR/VGPR/PR/MR/PD Will be categorized as NE for ORR analysis. For ORR analysis in IA, the UC response (PR or better) will be counted as responder.
13	PD (due to reasons other than imaging, i.e., plasmacytoma or bone lesion)	PD (any reason) including PD after initiation of new anti-cancer therapy OR	PD

	Response at the First Time Point	Response at Subsequent Time Point¹	Confirmed Response at the First Time Point
		No subsequent disease assessment: subject died due to PD before further adequate disease assessment (including death due to PD after initiation of new anti-cancer therapy)	
14	PD (due to reasons other than imaging, i.e., plasmacytoma or bone lesion)	sCR/CR/VGPR/PR/MR/SD OR No subsequent disease assessment: subject died due to reasons other than PD before further adequate disease assessment OR No subsequent disease assessment: subject discontinued study before further adequate disease assessment	NE
15	SD	Any OR No subsequent disease assessment	SD
16	PD due to imaging (plasmacytoma or bone lesion)	Any OR No subsequent disease assessment	PD
17	NE or missing	Any OR No subsequent disease assessment	NE

1 Subsequent disease assessment is defined as the next adequate (not missing or NE) disease assessment following the first timepoint before (or on the same date of) start of new anti-cancer therapy except for confirmation of PD, for which PD or death due to PD after new anti-cancer therapy are considered for confirmation of PD. No minimal time interval is required for the subsequent disease assessment but a different sample is required for confirmation.

2 SD does not need to be confirmed.

3 PD due to imaging (i.e., plasmacytoma or bone lesion) does not need to be confirmed.

Where criteria are not mutually exclusive, take the first that applies.

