7.2.2. Secondary Efficacy Analyses

7.2.2.1. Endpoint / Variables

CBR

Clinical Benefit Rate (CBR), defined as the percentage of participants with a confirmed MR or better (i.e., MR, PR, VGPR, CR and sCR) as the BOR assessed by the investigator per IMWG (2016).

DOR

Duration of response (DoR), defined as the interval of time (in months) from first documented evidence of confirmed PR or better to the time when disease progression is documented assessed by the investigator per IMWG (2016), or death due to PD among participants with a confirmed PR or better as the BOR. Responders without confirmed PD will be censored at the censoring time point for time to progression as specified in [Table 6](#).

TTR

Time to response (TTR), defined as the interval of time (in months) between the date of first dose and the first documented evidence of response (PR or better) among participants with a confirmed PR or better as the BOR assessed by the investigator per IMWG (2016).

TTBR

Time to best response (TTBR), defined as the interval of time (in months) between the date of first dose and the earliest date of achieving BOR among participants with a confirmed PR or better as the BOR assessed by investigator per IMWG (2016).

PFS

Progression-free survival (PFS), defined as the interval of time (in months) from first dose until the earlier date of disease progression per IMWG (2016), or the date of death due to any cause. Determination of dates of PFS events and dates for censoring are described in [Table 5](#).

TTP

Time to disease progression (TTP), defined as the interval of time (in months) from first dose until the earlier date of PD per IMWG (2016), or the date of death due to PD. Determination of dates of TTP events and dates for censoring are described in [Table 6](#).

OS

Overall Survival (OS), defined as the interval of time (in months) from first dose to the date of death due to any cause. Participants who withdraw consent from the study or are lost to follow-up will be censored at the time of withdrawal or lost to follow-up. Participants who do not have a death record at the clinical cut-off date for the analysis will be censored at the last known alive date. The last contact date will be determined by

the maximum collection/assessment date from among selected data domains within the clinical database.

Table 5 Assignments of Progression and Censoring Dates for PFS Analysis

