Situation	Date of Event (Progression/Death) or Censored ¹	Event (Progression/Death) Or Censored
No adequate baseline assessments ⁴ and the subject has not died (if the subject has died follow the rules for death indicated at the bottom of the Table)	First dose	Censored
No post-baseline assessments and the subject has not died (if the subject has died follow the rules for death indicated at the bottom of the Table)	First dose	Censored
Progression documented between scheduled visits	Date of assessment of progression	Event
With post-baseline assessment but no progression (or death)	Date of last 'adequate' assessment of response ²	Censored
No adequate post-baseline assessment before start of new anticancer therapy	First dose	Censored
With adequate post-baseline assessment and new anticancer treatment started (prior to documented disease progression). ³	Date of last 'adequate' assessment of response ² (on or prior to starting anti-cancer therapy)	Censored
Death before first scheduled assessment (or Death at baseline or without any adequate assessments)	Date of death	Event
Death between adequate assessment visits	Date of death	Event
Death or progression after more than three missed scheduled assessment	Date of last 'adequate' assessment of response ² (prior to missed assessments): If the disease assessment is every 3 weeks, a window of 66 days (9 weeks + 3 day window) will be used to determine whether there is extended time without adequate assessment. If the time difference between PD/death and last adequate disease assessment is more than 66 days, PFS will be censored at the last adequate disease assessment prior to PD/death.	Censored

¹ Event or censored are based on confirmed responses.

² An adequate assessment is defined as an unconfirmed assessment where the investigator assessed response is sCR, CR, PR, VGPR, MR, or SD.

³ If PD and New anti-cancer therapy occur on the same day assume the progression was documented first e.g., outcome is progression and the date is the date of the assessment of progression).

⁴ Adequate baseline assessment is defined as at baseline, a patient has at least one of the following measurements: a. Serum M-protein ≥ 0.5 g/dL (≥ 5 g/L) or b. Urine M-protein ≥ 200 mg/24h or c. Serum FLC assay: Involved FLC level ≥ 10 mg/dL (≥ 100 mg/L) and an abnormal serum free light chain ratio (< 0.26 or > 1.65).

Table 6 Assignments for Progression and Censoring Dates for TTP Analysis

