Situation	Date of Event (Progression/Death due to PD) or Censored ¹	Event (Progression/Death due to PD) Or Censored
No adequate baseline assessments ⁴ and the subject has not died (if the subject has died due to PD follow the rules for death indicated at the bottom of the Table)	First dose	Censored
No post-baseline assessments and the subject has not died (if the subject has died due to PD follow the rules for death due to PD indicated at the bottom of the Table)	First dose	Censored
Progression documented between scheduled visits	Date of assessment of progression	Event
With post-baseline assessment but no progression (or death due to PD)	Date of last 'adequate' assessment of response ²	Censored
No adequate post-baseline assessment before start of new anticancer therapy	First dose	Censored
With adequate post-baseline assessment and new anticancer treatment started (prior to documented disease progression). ³	Date of last 'adequate' assessment of response ² (on or prior to starting anti-cancer therapy)	Censored
Death due to PD before first scheduled assessment (or Death at baseline or without any adequate assessments)	Date of death	Event
Death due to PD between adequate assessment visits	Date of death	Event
Death from causes other than PD before first scheduled assessment (or Death at baseline or without any adequate assessments)	Date of death	Censored
Death from causes other than PD between adequate assessment visits	Date of death	Censored
Death due to PD or progression after more than three missed scheduled assessment	Date of last 'adequate' assessment of response ² (prior to missed assessments): If the disease assessment is every 3 weeks, a window of 66 days (9 weeks + 3 day window) will be used to determine whether there is extended time without adequate assessment. If the time difference between PD/death due to PD and last adequate disease assessment is	Censored

CONFIDENTIAL

205207

Situation	Date of Event (Progression/Death due to PD) or Censored ¹	Event (Progression/Death due to PD) Or Censored
	more than 66 days, PFS will be censored at the last adequate disease assessment prior to PD/death due to PD.	

¹ Event or censored are based on confirmed responses.

² An adequate assessment is defined as an assessment where the investigator assessed response is sCR, CR, PR, VGPR, MR, or SD .

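### Row 1 of Tables 5 and 6, read literally, censors a living subject at first dose despite documented progression, and can give a censored responder a negative duration of response

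*SAP*

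**What the plan says.** Row 1 of Table 5 applies to a subject with no adequate baseline assessment "and the subject has not died (if the subject has died follow the rules for death indicated at the bottom of the Table"), and assigns first dose, censored. Row 1 of Table 6 does the same for TTP, with the exemption worded as "if the subject has died due to PD follow the rules for death indicated at the bottom of the Table".

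Footnote 4 to both tables sets the test: "Adequate baseline assessment is defined as at baseline, a patient has at least one of the following measurements", followed by serum M-protein of at least 0.5 g/dL, urine M-protein of at least 200 mg/24h, or involved FLC of at least 10 mg/dL with an abnormal ratio. It is a threshold on the value. A complete baseline work-up below all three limits does not pass. Under Section 5.2, "the baseline value will be the latest pre-dose assessment with a non-missing value".

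The one row that makes progression an event is headed "Progression documented between scheduled visits". Section 7.2.2.1 defines PFS and TTP from first dose to progression or death (for TTP, death due to PD), with no condition on baseline level. The population is All Treated (Section 7.2.2.3), which Section 4 defines by one dose.

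For DoR, Section 7.2.2.1 says: "Responders without confirmed PD will be censored at the censoring time point for time to progression as specified in" Table 6.

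**The concern.** The death-only exemption suits row 2, because a subject with no post-baseline assessment cannot have assessed progression. In row 1 the subject may have a full series of assessments, so progression can be on record and still be set aside. Imaging progression shows this most clearly. Table 4 has a row for "PD due to imaging (plasmacytoma or bone lesion") and counts it without confirmation, and it does not depend on an M-protein or FLC level.

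Table 4 also sets no baseline threshold for response, so on the SAP's text a subject who meets row 1 can be a confirmed responder. If that responder has not progressed, DoR starts at the response and is censored at first dose, which is earlier. At stake are lost events and lost follow-up in PFS and TTP, impossible DoR values, and the chance that two programmers code the same subject differently.

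**Working it through.** The plan gives no figure on this point to reproduce. The check applies the rows to three hypothetical living subjects without an adequate baseline.

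**Inputs**
- Row 1, the progression row and the row for post-baseline assessment without progression: Tables 5 and 6.
- DoR rule: Section 7.2.2.1.
- Maximum Part 2 size, 28: Section 3.1.2.1.
- Assumed for illustration: first dose on Day 1, the assessment days below (all on a three-weekly grid from Day 1), and 30.4375 days per month. DoR is end day minus response day.

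**Which rows match**
- *Subject A: progression on Day 127, no response.* Row 1 gives Day 1, censored. The progression row, if read to cover any visit, gives Day 127, event. If Day 127 is a scheduled visit and that row is read as worded, only row 1 matches.
- *Subject B: first PR on Day 43, no progression, last adequate assessment on Day 400.* Row 1 gives Day 1, censored. The no-progression row gives Day 400, censored. DoR is 1 - 43 = -42 days (-1.4 months) under row 1, and 400 - 43 = 357 days (11.7 months) under the other.
- *Subject C: first PR on Day 43, confirmed progression on Day 253.* The DoR sentence sends only responders without confirmed progression to Table 6, so DoR is an event at 253 - 43 = 210 days (6.9 months). TTP for the same subject is censored on Day 1 under row 1.

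**Other response days, DoR censored at first dose**
- Day 22: 1 - 22 = -21 days
- Day 64: 1 - 64 = -63 days
- Day 85: 1 - 85 = -84 days (-2.8 months)

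**Precedence.** The note "Where criteria are not mutually exclusive, take the first that applies" belongs to Table 4. Tables 5 and 6 carry no such note. If it were borrowed, it would select row 1.

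**Share of Part 2.** Each subject coded by row 1 contributes no PFS or TTP follow-up. The number is not given. If it were 1, 2 or 3 of 28, the share would be 1/28 = 3.6%, 2/28 = 7.1% or 3/28 = 10.7%.

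**The case against.** The strongest reply is that the rows overlap and row 1 need not win. A living subject with progression can also be placed in the progression row, and a living responder without progression in the no-progression row. Both definitions count progression without a baseline condition. Taken literally, the progression row would miss progression at a scheduled visit for every subject, so a broader meaning was probably intended. This stands: a reader might infer that the tables certainly censor every living subject below the measurable level, and the text does not establish that. It does not clear the tables. The explicit carve-out for death would be needless if later rows overrode row 1, and nothing says which row prevails.

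The reply on frequency also stands. Eligibility and the sampling schedule are left to the protocol. A subject who met a limit at screening falls into row 1 only if serum, urine and FLC criteria all fail on the later pre-dose values. Whether the cited response criteria allow a confirmed PR without a measurable baseline cannot be checked from the SAP. The interim display footnotes in Appendix 11 mention adequate baseline and measurable disease, but only for the All Evaluable population.

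Censoring at first dose when no baseline exists at all is a common convention and is not at issue here.

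**Conclusion.** The point holds as a defect in stated rules. Row 1, read literally, removes documented progression from PFS and TTP in a living subject with a sub-measurable baseline. On the most favourable reading, the tables give two answers without choosing. The DoR sentence, combined with row 1, can produce a negative duration because no floor at the response date is stated.

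The size is unknown and may be zero. The 1 to 3 of 28 above is an assumption. PFS, TTP and DoR are secondary and descriptive in a single-arm study, and ORR is unaffected.

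Three stronger inferences are not supported:
- *That progressions are lost from DoR.* Responders with confirmed progression keep a DoR event; the inconsistency is with their TTP. The lost progressions and the negative durations arise in different subjects.
- *That 6-month PFS rises by 3.6 points per affected subject (10.7 for three).* This needs progression before month 6 and a death counted as an event after it. The 66-day row counts a death only within 66 days of the last adequate assessment, which by footnote 2 is not a PD assessment. With month 6 at about Day 183, that assessment must fall on about Day 117 or later (183 - 66). It also assumes no earlier censoring.
- *That the endpoints use different populations.* ORR, PFS and TTP all use All Treated, and DoR is limited to responders by definition. Subjects censored at first dose remain in the population but add no follow-up.

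**What to change.** - In row 1 of both tables, add the condition that there is no documented PD (imaging PD, or PD confirmed per Table 4).
- Reword the progression row to cover PD documented at any visit, still subject to the new-therapy and 66-day rows.
- Add a precedence rule to Tables 5 and 6.
- State that DoR is never censored before the first response date, and that the last adequate assessment is used instead.

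Keep the Section 5.2 baseline definition; judging adequacy on any screening value would be a preference and would depart from it.

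The cost is SAP wording and a small programming change. The small downside is that a few PD events may rest on a sub-measurable baseline. Flag these in the PFS and TTP listings.

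### In SAP Tables 5 and 6 the first-dose censoring row for new therapy has no progression limit, so with footnote 2 a first-assessment PD followed by new therapy is censored at first dose, against the PFS and TTP definitions

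*SAP*

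**What the plan says.** Section 7.2.2.1 defines PFS as the time "from first dose until the earlier date of disease progression per IMWG (2016), or the date of death due to any cause". TTP is defined in the same way, with death due to PD in place of death from any cause. Event and censoring dates are delegated to Table 5 (PFS) and Table 6 (TTP).

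The following apply in both tables unless stated:

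- **Disputed row:** "No adequate post-baseline assessment before start of new anticancer therapy". Date: first dose. Status: censored.
- **Next row:** "With adequate post-baseline assessment and new anticancer treatment started (prior to documented disease progression"). Date: last adequate assessment on or before the new therapy. Status: censored.
- **Progression row:** "Progression documented between scheduled visits". Date: assessment of progression. Status: event.
- **Footnote 2, Table 5:** "An adequate assessment is defined as an unconfirmed assessment where the investigator assessed response is sCR, CR, PR, VGPR, MR, or SD". Table 6 gives the same list: "An adequate assessment is defined as an assessment where the investigator assessed response is sCR, CR, PR, VGPR, MR, or SD".
- **Footnote 3:** "If PD and New anti-cancer therapy occur on the same day assume the progression was documented first". Its marker stands only on the next row.

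Table 4 (Section 7.1.1.1) also bears on the point. Row 13 lets a laboratory PD be confirmed by a further PD, or by death due to PD, after new therapy has begun. Row 16 accepts imaging PD without confirmation. Note 1 treats an assessment as adequate when it is neither missing nor not evaluable.

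**The concern.** PD is a valid post-baseline assessment and ends PFS and TTP, but footnote 2 does not count it as adequate. For choosing a censoring date that is sensible. Carried into the condition of the disputed row, it turns an observed early event into censoring at time zero. The next row avoids this through its progression limit; the disputed row has no such limit.

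The subjects concerned are those with primary-refractory disease, who contribute the earliest events and have a clear reason to change treatment. Removing them at day 0 can only make PFS and TTP look better. PFS is a headline display (Table 2.007 in Section 16.11.5), and Section 7.2.2.2 plans both the median and the 6-month rate.

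**Working it through.** The plan states no PFS or TTP figure to reproduce, so the check has two parts.

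**1. Rule logic.** Take a subject with measurable disease at baseline whose first post-baseline assessment is PD. The PD is either on imaging, or on laboratory values and confirmed under Table 4.

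- *PD at a scheduled visit, then new therapy.* With footnote 2, no adequate assessment precedes the therapy, so the disputed row applies: censored at first dose. The progression row, read literally, names only PD between visits. The next row does not apply because it requires an adequate assessment.
- *PD between scheduled visits, then new therapy.* The progression row (event at PD) and the disputed row (censored at first dose) both apply. The rule to take the first criterion that applies is printed under Table 4 only.
- *Either case, followed by death.* In Table 5 the row for death without any adequate assessment also applies, giving an event at the date of death. In Table 6 that holds for death due to PD. This is a further conflict with no tie-break.
- *PD without new therapy.* The disputed row does not apply.
- *Meaning of adequate taken from Table 4 note 1.* PD is adequate, so the disputed row does not apply.

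**2. Size if the row is applied with footnote 2.** Inputs from the SAP: 28 subjects (Section 3.1.2.1), 3-weekly assessment (the interval used in Tables 5 and 6), about 15 months of follow-up (Section 2.3). Assumptions, not document figures: exponential PFS with median m = 2, 4 or 6 months; every first-interval event is a PD; a fraction f = 0.8 or 0.5 of these subjects start new therapy.

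The first visit is at 21/30.4375 = 0.690 months.

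- Probability of an event by the first visit: p = 1 − 2^(−0.690/m).
- Subjects censored at first dose: k = 28 × p × f.
- The last visit before 6 months is day 168 (5.52 months), so the 6-month PFS with PD counted is S = 2^(−5.52/m).
- The k subjects leave the risk set at day 0 and nobody else is censored before 6 months, so the 6-month PFS under the row is S × 28/(28 − k).

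| m (months) | p | S, PD counted | k, f = 0.8 | PFS under the row | k, f = 0.5 | PFS under the row |
|---|---|---|---|---|---|---|
| 2 | 0.213 | 14.8% | 4.76 | 17.8% | 2.98 | 16.5% |
| 4 | 0.113 | 38.4% | 2.52 | 42.2% | 1.58 | 40.7% |
| 6 | 0.077 | 52.9% | 1.72 | 56.3% | 1.07 | 55.0% |

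The gain is 3 to 4 points at f = 0.8 and about 2 points at f = 0.5. Simulating 3,000 trials per scenario gave the same 6-month rates to within about 0.2 points. The median rose by 0.57 to 0.68 months at f = 0.8 and by 0.38 to 0.49 months at f = 0.5.

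The shift depends on k. With exactly 4 of 28 subjects affected and the other 24 following a curve with a 5-month median, 10 subjects are progression-free at 6 months: 10/28 = 35.7% with the PDs counted, 10/24 = 41.7% under the row.

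**The case against.** The strongest reply is that the documents do not force the harmful reading.

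- The footnote 2 marker stands on the date column, where it selects a censoring date. It is not on the disputed row, and Table 4 note 1 gives a meaning of adequate that includes PD.
- The definitions, footnote 3 and Table 4 row 13 all point towards counting PD that precedes new therapy. The neighbouring censoring rows are confined to subjects without progression.
- A reader might infer that PD at a scheduled visit is never an event. That proves too much: almost no progression would then count, with or without new therapy. The row more plausibly says that even an off-schedule PD takes its own date.
- The size rests on assumed rates. The illustration also treats early deaths as PD and ignores the death rows.
- PFS and TTP are secondary and descriptive, and Listing 1.0017 would show a first-dose censoring.

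Most of this stands. It shows that the intent is probably to count these events, and that the figures are not an expected bias. It does not remove the defect. Footnote 2 is worded as a general definition within each table, the disputed row uses the defined word, and the limit is missing where the next row has it. Even with the progression row read broadly, two rows with opposite outcomes apply and nothing ranks them.

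**Conclusion.** The point holds as a drafting defect in a censoring rule. Applied with the tables' own footnote, the row gives an event status that contradicts the PFS and TTP definitions and Table 4, always in the favourable direction. A reader might go further and conclude that the plan unambiguously discards every early progression. The documents do not support that: another meaning of adequate is available in Table 4, PD between visits also meets an event row, and later deaths meet their own rows.

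Conditional on the footnote 2 reading, 6-month PFS rises by about 2 to 4 points and the median by roughly 0.4 to 0.7 months. This assumes 28 subjects, true medians of 2 to 6 months and 50% to 80% of first-visit progressors starting new therapy. For those inputs it is an upper-end figure, because every first-interval event is taken as PD and the row is applied to every such subject. A larger cluster of first-visit progressors would shift it further. ORR, the only endpoint with a hypothesis, is unaffected. DoR is hardly affected, because responders have an adequate assessment.

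**What to change.** In both tables:

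1. Limit the disputed row to subjects with no documented progression or death on or before the start of new therapy (in Table 6, death due to PD).
2. Reword the progression row so that it covers PD found at a scheduled visit as well as between visits.
3. State that PD documented per Table 4 on or before the start of new therapy takes precedence over the new-therapy first-dose censoring row.

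The cost is SAP wording and the matching program specification, with no new data and no design change. Compared with the footnote 2 reading, PFS and TTP become slightly less favourable; if the programs already count these PDs, no result changes.
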